## **Background**

- NPC has a uniquely high prevalence in Southern China. According to the Hong Kong Cancer Registry in 2012, NPC was the sixth commonest cancer in men and thirteenth in women. It accounted for 2.9% of all new cancer cases. In 2012, there were 819 new cases of NPC.
- NPC is highly radiosensitive. Radiotherapy and chemotherapy are the mainstay of treatment. Despite the chemo-irradiation, disease control failure still occurred in NPC patients presenting as persistent tumor. Early detection of those post-radiotherapy residual NPC is essential for early arrangement of salvage therapy. Detection methods include imaging, plasma Epstein-Barr virus DNA, endoscopy examinations and nasopharynx biopsy.
- Narrow Band Imaging (NBI) is an optical image enhancement technology that improves the visibility of blood vessels. White light is composed of an equal mixture of wavelengths. The shorter wavelengths only penetrate the top layer of the mucosa, while the longer wavelengths penetrate deep into the mucosa. NBI light is composed of just two specific wavelengths that are strongly absorbed by hemoglobin: blue light (415 nm) and green light (540 nm). This wavelength allows a better understanding of the vasculature of suspect lesions.
- NBI system has been well proven as a tool to detect early digestive tract cancer and head and neck cancer. However, there were only few studies targeting the detection of post-radiotherapy mucosal residual of NPC using NBI system

## **Objective**

1. To identify the vessel pattern of those confirmed NPC case using NBI system
2. To identify the endoscopy features of post-radiotherapy mucosal residual nasopharyngeal carcinoma using NBI system
3. To establish the positive predicted value, negative predicted value, sensitivity and specificity of using both normal white light (WL) endoscopy and NBI system for detecting mucosal residual NPC

## **Design**

- Prospective cross sectional study

## **Study Period:**

- 12/2015 – 12/2016 for case recruitment
- Every patient follow up time around 4 months ( till 4/2017)
- Present at College Annual Scientific Meeting in 11/2017

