### **Exclusion Criteria**

- History of radiotherapy to head and neck region
- Poor premorbid status/ non-communicable patients
- <18 years old
- Pregnancy

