### **Method**

- 1 A New ENT NBI clinic **is established and held** on every Friday pm (preferably) and Wednesday am (in case the patient is not available on Friday pm session or Friday is a public holiday)
- 2 Newly biopsy confirmed NPC patient
  - 2.1 Department of ENT: All biopsy confirmed NPC patients will be called back to the NBI clinic. They will be assessed by [name] and a complete ENT examination would be performed. Patient will undergo endoscopy examination (both WL + NBI), endoscopy image will be stored in the ePR system, consent forms will be signed and, baseline pure tone audiogram will be arranged. Patients will also be referred to oncology department.
  - 2.2 Department of Oncology: All new biopsy confirmed NPC patients **will be referred to ENT NBI clinic**. They will be assessed by [name] and a complete ENT examination would be performed. Patient will undergo endoscopy examination (both WL + NBI), endoscopy image will be stored in the ePR system, consent forms will be signed and, baseline pure tone audiogram will be arranged.
- 3 All patients will be followed up by both oncology and ENT department (**in ENT general clinic**) together regularly and look for chemo-radiation complication and hearing impairment.
- 4 At post-radiotherapy (2nd weeks) follow up in oncology department
  - 4.1 An appointment at post-radiotherapy 8th weeks will be arranged for the ENT NBI clinic (preferably on Friday pm) to perform nasopharynx biopsy
  - 4.2 An appointment at post-radiotherapy 10th weeks will be arranged for the oncology clinic to review biopsy result
- 5 At post-radiotherapy 8th weeks NBI clinic: The patient will undergo endoscopy examination (both WL and NBI) and nasopharyngeal biopsy will be taken. All the images will be saved in ePR. The consultation note template will be as same as the oncology endoscopy session template.
- 6 Biopsy results will be reviewed by oncology colleagues at the post-radiotherapy 10th weeks clinic

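### Does follow-up of about four months, ending 4/2017, cut off late-2016 recruits before their post-radiotherapy biopsy?

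*Protocol*

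**What the plan says.** The Study Period section of the Protocol sets "12/2015 – 12/2016 for case recruitment" and then "Every patient follow up time around 4 months ( till 4/2017". Results are to be presented in 11/2017.

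Patients enter untreated. The Exclusion Criteria rule out "History of radiotherapy to head and neck region", and Method item 2.1 says "All biopsy confirmed NPC patients will be called back to the NBI clinic" for the baseline examination, with oncology referral alongside.

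The accuracy data come later. At the clinic 8 weeks after radiotherapy (Method item 5), "The patient will undergo endoscopy examination (both WL and NBI) and nasopharyngeal biopsy will be taken". Item 6 adds "Biopsy results will be reviewed by oncology colleagues at the post-radiotherapy 10th weeks clinic". The SAP then cross-tabulates suspicious versus non-suspicious NBI pattern against residual disease status, so a patient needs both the week-8 endoscopy and the biopsy result to be counted.

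On treatment, the Background says only "Radiotherapy and chemotherapy are the mainstay of treatment". Neither document states how long patients wait for radiotherapy, how long the course lasts, or whether chemotherapy precedes it.

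**The concern.** Set side by side, the dates look inconsistent. A patient recruited at the end of December 2016 still has to be seen by oncology, wait for treatment, complete radiotherapy and then reach weeks 8 and 10, all by April 2017. Counting the four months from the end of radiotherapy does not remove the difficulty. An end in 4/2017 would then require radiotherapy to have finished by about 12/2016, while untreated patients are still being recruited that month.

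If the data really closed in April 2017, late recruits would have a baseline examination but no reference-standard result and would drop out of the 2x2 table. The target of 50-70 is stated as new cases, not as cases with an outcome, and no rule covers a patient without a week-8 biopsy. If those lost were the slowest to finish treatment, and slowness went with more extensive disease, the residual rate and the predictive values could shift.

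**Working it through.** **Inputs from the Protocol.** Recruitment 12/2015 to 12/2016; follow-up about 4 months, to 4/2017; biopsy at week 8 and result at week 10 after radiotherapy; target 50-70; presentation 11/2017.

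**Assumptions (not in the documents).** Radiotherapy of 6-7 weeks; wait from entry to start of 0-8 weeks; even accrual from 1 December 2015 to 31 December 2016 (396 days); 4/2017 read as 30 April 2017 unless stated.

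**1. The plan's own date.** 12/2016 + 4 months = 4/2017. The figure reproduces, and it suggests that the four months run from recruitment.

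**2. Time available.** 4 × 30.44 / 7 = 17.4 weeks.
- Before the week-8 clock: 17.4 − 8 = 9.4 weeks.
- Before the week-10 clock: 17.4 − 10 = 7.4 weeks.

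By calendar to 30 April 2017, entry on 31 December 2016 gives 17.1 weeks (9.1 and 7.1 left). Entry on 1 December gives 21.4 weeks (13.4 and 11.4 left).

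**3. Time needed to the week-10 result.** Wait + radiotherapy + 10.
- No wait: 16-17 weeks. A 31 December entrant reaches week 10 between 22 and 29 April 2017, inside the window.
- 2-week wait: 18-19 weeks.
- 4-week wait: 20-21 weeks.
- 8-week wait: 24-25 weeks, so the last entrant's result comes in mid to late June 2017.

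**4. Share without a result by 30 April 2017.** Share = (days from the last workable entry date to 31 December 2016) / 396. With 7 weeks of radiotherapy:

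| Wait | Total to week 10 | Last workable entry | Share | Of 50-70 |
|---|---|---|---|---|
| 0 weeks | 17 weeks | 1 Jan 2017 | 0% | 0 |
| 2 weeks | 19 weeks | 18 Dec 2016 | 13/396 = 3.3% | 1.6-2.3 |
| 4 weeks | 21 weeks | 4 Dec 2016 | 27/396 = 6.8% | 3.4-4.8 |
| 8 weeks | 25 weeks | 6 Nov 2016 | 55/396 = 13.9% | 6.9-9.7 |

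If only the week-8 biopsy has to fall inside the window, each total is two weeks shorter. The shares become 0%, 0%, 3.3% and 10.4%.

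**5. Harsher assumptions.**
- Thirty weeks from entry to result gives 90/396 = 22.7%, or 11 to 16 patients.
- Closing on 1 April instead of 30 April moves the last workable entry to 3 December (17 weeks) or 8 October 2016 (25 weeks). The shares are 28/396 = 7.1% and 84/396 = 21.2%.

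**6. What a strict cut-off would cost.** If all cells shrink in proportion, standard errors grow by 1/√(1 − share). At 13.9% this is 1/√0.861 = 1.08; at 22.7% it is 1/√0.773 = 1.14. Intervals would be 8% to 14% wider.

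**7. Room to wait.** At 30 weeks, a 31 December 2016 entrant has a result on 29 July 2017. From 31 December 2016 to 1 November 2017 is 43.6 weeks, so even this slow case leaves 43.6 − 30 = 13.6 weeks before the month of presentation.

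**The case for a change.** The strongest case for a change is that only a near-zero wait avoids loss, and that is hard to square with Method item 2.1, where patients seen in ENT are still to be referred to oncology after the diagnosis. The Background and Method also mention combined chemotherapy and radiation, so some patients may have drug treatment first. Neither reading of the four months fits every December entrant comfortably. A line tying the end of follow-up to the last patient's week-10 review would cost almost nothing.

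Much of this stands. The starting point of the four months is not stated, the slack for entrants from about November and December 2016 is thin, and some result dates may well fall after April 2017.

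The step from there to lost outcomes does not stand. It needs a rule that closes the data in April 2017, and there is none. The bias argument is weaker still. Under a calendar cut-off, loss depends first on late entry, and slow treatment matters only among late entrants. The documents give no link between treatment time and residual disease. Since the suggested line records what the investigators would do in any case, its low cost does not make it necessary.

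**Conclusion.** No change is called for. This is an approximate planning date with little slack, not a contradiction that would produce a wrong result. Method items 4 to 6 time the endoscopy, biopsy and review from the end of radiotherapy, so a late recruit's visits simply fall later. With presentation in 11/2017, analysts would wait for the last biopsies, and there is room to do so even at 30 weeks from entry to result.

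Were the data closed on 30 April 2017 all the same, the loss would be 0% to 14% (0 to about 10 of 50-70) under the assumed 7 weeks of radiotherapy and 0-8 week wait. That would give a somewhat smaller sample and intervals up to about 8% wider. Longer treatment paths or an earlier closing day push the loss to roughly 21-23%. These sizes rest on assumed treatment times and even accrual. The conclusion that no outcome need be lost rests on what the Protocol does say: the visits are tied to radiotherapy, and nothing excludes later results.

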### **Inclusion Criteria**

- New NPC patient

### **Exclusion Criteria**

- History of radiotherapy to head and neck region
- Poor premorbid status/ non-communicable patients
- <18 years old
- Pregnancy

### **Method**

- 1 A New ENT NBI clinic **is established and held** on every Friday pm (preferably) and Wednesday am (in case the patient is not available on Friday pm session or Friday is a public holiday)
- 2 Newly biopsy confirmed NPC patient
  - 2.1 Department of ENT: All biopsy confirmed NPC patients will be called back to the NBI clinic. They will be assessed by [name] and a complete ENT examination would be performed. Patient will undergo endoscopy examination (both WL + NBI), endoscopy image will be stored in the ePR system, consent forms will be signed and, baseline pure tone audiogram will be arranged. Patients will also be referred to oncology department.
  - 2.2 Department of Oncology: All new biopsy confirmed NPC patients **will be referred to ENT NBI clinic**. They will be assessed by [name] and a complete ENT examination would be performed. Patient will undergo endoscopy examination (both WL + NBI), endoscopy image will be stored in the ePR system, consent forms will be signed and, baseline pure tone audiogram will be arranged.
- 3 All patients will be followed up by both oncology and ENT department (**in ENT general clinic**) together regularly and look for chemo-radiation complication and hearing impairment.
- 4 At post-radiotherapy (2nd weeks) follow up in oncology department
  - 4.1 An appointment at post-radiotherapy 8th weeks will be arranged for the ENT NBI clinic (preferably on Friday pm) to perform nasopharynx biopsy
  - 4.2 An appointment at post-radiotherapy 10th weeks will be arranged for the oncology clinic to review biopsy result
- 5 At post-radiotherapy 8th weeks NBI clinic: The patient will undergo endoscopy examination (both WL and NBI) and nasopharyngeal biopsy will be taken. All the images will be saved in ePR. The consultation note template will be as same as the oncology endoscopy session template.
- 6 Biopsy results will be reviewed by oncology colleagues at the post-radiotherapy 10th weeks clinic

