### **Analysis**

- Results will be process and analyzed as mean +/- standard deviation for continuous variables, and percentage for categorical variable.
- Positive predicted value, negative predicted value, sensitivity, specificity of both white light and NBI system will be calculated

- Statistical difference will be compared by chi-square test. P<0.05 was set as statistically significant
- Statistical analysis will be carried out with SPSS version 13

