Title:

Using narrow-band imaging (NBI) technique to detect post-radiotherapy mucosal residual nasopharyngeal carcinoma (NPC)

Principle Investigator

[name] [name],

Statistical Analysis plan

1. Post-RT NP NBI vessel pattern were analyzed
2. Vessel pattern will be divided into NBI suspicious group and NBI non suspicious group
3. 2x2 table of suspicious/ non-suspicious group vs no residual disease / have residual disease will be obtained
4. Chi-square test will be performed, p-value will be contained
5. Sensitivity, specificity, positive predicted value, negative predicted value of using NBI to detect mucosal residual NPC will be calculated

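### White light and NBI are viewed in one week-8 session with no set order, separate white light entry or blinding, so influence of NBI on the white light accuracy figures cannot be excluded

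*Protocol*

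**What the plan says.** Objective 3 of the protocol is to establish predictive values, sensitivity and specificity of "using both normal white light (WL) endoscopy and NBI system for detecting mucosal residual NPC". The Analysis section repeats this: "Positive predicted value, negative predicted value, sensitivity, specificity of both white light and NBI system will be calculated". It continues: "Statistical difference will be compared by chi-square test. P<0.05 was set as statistically significant", without naming the two things to be compared.

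Method item 5 describes the week-8 visit: "The patient will undergo endoscopy examination (both WL and NBI) and nasopharyngeal biopsy will be taken". Two recording provisions follow: "All the images will be saved in ePR", and "The consultation note template will be as same as the oncology endoscopy session template". The template itself is not in the documents. Under Method item 6, oncology reviews the biopsy result at week 10.

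The SAP deals with NBI only. Item 2 reads: "Vessel pattern will be divided into NBI suspicious group and NBI non suspicious group". Item 3 cross-tabulates those groups with residual disease, item 4 applies a chi-square test, and item 5 reads: "Sensitivity, specificity, positive predicted value, negative predicted value of using NBI to detect mucosal residual NPC will be calculated". WL is not mentioned, and no time, grader or blinding is given for the grouping.

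**The concern.** Separate accuracy figures for two tests on the same patient need two separate calls, and the WL call should not depend on what NBI showed. Here both views are available in one sitting, and no step fixes the WL call before NBI is seen.

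Two opposite effects are possible. An examiner who sees a suspicious vessel pattern on NBI may look again and call WL suspicious too; WL accuracy then moves towards that of NBI and a real difference is hidden. An examiner who expects NBI to do better may leave WL as non-suspicious and let NBI carry the finding; WL sensitivity then looks lower than it is. The direction cannot be known from the results.

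A related gap affects NBI. The grouping is listed as an analysis step, next to a table that needs the histology result. If grading were done with histology known, the NBI figures would tend to be too favourable.

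**Working it through.** No figure in the documents depends on reading order. The target of 50-70 new cases comes with no power, prevalence or expected accuracy, so there is nothing to reproduce. The check is of the text, followed by an illustration in which every input is assumed.

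**Step 1: what is needed against what is provided**

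- Needed for each patient: one WL call, one NBI call, one histology result (Objective 3; Analysis).
- Provided for WL: the week-8 view, saved images and a reused note template. There is no viewing order, named reader per mode, criterion for a suspicious WL finding, or WL table in the SAP.
- Provided for NBI: a suspicious / non-suspicious split (SAP item 2) and a table (SAP item 3), with no date, grader or blinding.
- Timing: the biopsy is taken at the same visit as the two views, so any call written down at that visit precedes histology. A grouping made at the analysis stage need not.

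**Step 2: how carry-over from NBI acts**

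Among patients with the same histology, let a be the probability that NBI is suspicious and WL is not, and b the reverse. The difference between the modes is a - b. If a fraction f of discordant WL calls is switched to the NBI call, a becomes a(1 - f) and b becomes b(1 - f), so the observed difference is (a - b)(1 - f). Equivalently, observed WL sensitivity = (1 - f) x true WL + f x NBI, and likewise for specificity. Under this model the factor (1 - f) applies whatever the inputs.

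**Step 3: numbers, all assumed**

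True sensitivity 0.50 for WL and 0.80 for NBI:

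| f | Observed WL sensitivity | Observed difference |
|---|---|---|
| 0 | 0.500 | 0.300 |
| 0.25 | 0.75 x 0.50 + 0.25 x 0.80 = 0.575 | 0.225 |
| 0.50 | 0.50 x 0.50 + 0.50 x 0.80 = 0.650 | 0.150 |
| 0.75 | 0.25 x 0.50 + 0.75 x 0.80 = 0.725 | 0.075 |
| 1 | 0.800 | 0 |

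Specificity moves too. With sensitivity / specificity of 0.60 / 0.90 for WL and 0.90 / 0.80 for NBI, f = 0.25 gives an observed WL of 0.675 / 0.875 and f = 0.5 gives 0.75 / 0.85.

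The opposite effect: if the examiner leaves WL as non-suspicious in a quarter of the residual cases that WL alone would have flagged, a WL sensitivity of 0.50 reads as 0.50 x 0.75 = 0.375. The difference from 0.80 then widens from 0.30 to 0.425.

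**Step 4: what this could do to a paired comparison**

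The plan names no paired test; exact two-sided McNemar power at the 0.05 level is used only as a yardstick.

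- 50 patients without residual tumour, 22% suspicious on WL only and 2% on NBI only, both multiplied by (1 - f): power 0.835, 0.657 and 0.349 at f = 0, 0.25 and 0.5. At an assumed residual rate of 5-20%, having 50 such patients takes 50 / 0.95 = 53 to 50 / 0.80 = 63 biopsied patients, above the lower target of 50.
- At the same assumed rates, the target gives 50 x 0.05 = 2.5 to 70 x 0.20 = 14 residual cases. With 14 cases, sensitivities of 0.50 and 0.80 and reads independent given histology (a = 0.40, b = 0.10), power is 21%, 11% and 3% at f = 0, 0.25 and 0.5.

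**The case against.** The strongest reply is that silence is not evidence of bias. WL may be viewed first in practice, and the template, which the reader cannot see, may already hold a separate WL entry. This stands: a reader might infer that the WL figures are contaminated, but the documents show only that they can be and that nothing written excludes it.

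Second, a reader might infer that an independent WL call is lost once both views have been seen. That is true only of the examiner who saw both. Because images are stored, another reader shown only the WL images and no histology could supply a call. No such re-read is planned, and still images may not reproduce the live examination.

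Third, a reader might infer that NBI is graded after histology. The SAP does not say so. Item 2 can be read as sorting vessel-pattern types into two groups, and results go to oncology at week 10, not to the NBI clinic. Grading with histology known is an inference from the lack of a date and a grader; it is simply not excluded. The SAP step concerns NBI, so it is no evidence about WL.

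Fourth, a head-to-head test of WL against NBI is the natural reading of the Analysis section but is not named there, and the SAP's chi-square test is of NBI group against residual disease. The risk to the separate WL figures does not depend on this.

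Finally, with few residual cases a sensitivity comparison would be weak even with clean readings: about 21% power in the 14-case illustration. That is a reason not to lean on the power figures. It does not remove the risk to the WL estimates.

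**Conclusion.** The concern holds as a gap in the plan. Separate WL and NBI accuracy is a stated objective, and the week-8 procedure has no order, separate WL entry before NBI, or blinding to support it. Following the plan as written can give a WL call shaped by the NBI view, and sensible choices at analysis alone cannot undo that. The SAP leaves open, without stating it, that NBI grouping is done with histology known.

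The size cannot be derived from the documents. The shrinkage by (1 - f) rests on the assumption that discordant WL calls move to the NBI call; f, the accuracies and the residual rate are all assumed, and the opposite direction is equally possible. The documents do not support saying that bias has occurred, or that the trial could not show whether NBI adds anything. The change is worth making because it protects a stated objective at almost no cost.

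**What to change.** Amend Method item 5 so that the week-8 template carries two mandatory binary fields, completed in this order and not editable later:

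1. WL suspicious / non-suspicious, entered before NBI is switched on.
2. NBI suspicious / non-suspicious, entered before the biopsy is taken.

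Each call should be made against a criterion written beforehand; neither document gives one for WL. If the existing template already has these fields, say so in the protocol and add the order and the lock.

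Amend the SAP to add a WL table against residual disease, with the same four accuracy measures as for NBI. State that the WL and NBI tables use the week-8 entries and not a later grading made with histology known. If a comparison of the two modes is intended, name it and make it paired. Vessel patterns can still be described from stored images under Objectives 1 and 2, but that description should not replace the entries in the accuracy tables.

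The cost is two fields, short additions to each document and a few seconds per examination, with no extra reader or procedure. The one downside is that with WL always first, the NBI call includes the WL view, so the NBI result should be described as NBI added to WL. For any patient without such entries, a re-read of stored images by separate readers unaware of the other mode and of histology is a second-best substitute, and it does need extra readers.

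### The week-8 biopsy is the only reference for residual disease and nothing checks a negative result, so missed tumour makes NPV too high and PPV and specificity too low; the effect on sensitivity is conditional

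*Protocol*

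**What the plan says.** Protocol, Method item 5, describes the week-8 visit after radiotherapy: "The patient will undergo endoscopy examination (both WL and NBI) and nasopharyngeal biopsy will be taken". Item 6 adds: "Biopsy results will be reviewed by oncology colleagues at the post-radiotherapy 10th weeks clinic". No other step in the Method establishes whether tumour remains. The Method does not state the biopsy site, the number of samples, what guides the sampling, or whether anyone is blinded to the NBI finding.

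SAP item 2 sets the index test: "Vessel pattern will be divided into NBI suspicious group and NBI non suspicious group". Item 3 sets the analysis: "2x2 table of suspicious/ non-suspicious group vs no residual disease / have residual disease will be obtained". Item 5 lists the results: "Sensitivity, specificity, positive predicted value, negative predicted value of using NBI to detect mucosal residual NPC will be calculated". The SAP neither defines residual disease nor mentions biopsy.

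Two other possible sources of information appear but are not used. The Protocol's Background says: "Detection methods include imaging, plasma Epstein-Barr virus DNA, endoscopy examinations and nasopharynx biopsy". Neither document uses imaging or viral DNA to set disease status. Method item 3 says: "All patients will be followed up by both oncology and ENT department", but the purpose it gives is to look for treatment complications and hearing loss. The Study Period section plans about 4 months of follow-up per patient, ending 4/2017, and then: "Present at College Annual Scientific Meeting in 11/2017".

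**The concern.** Accuracy figures are only as good as the column that says who has disease. With no definition in the SAP and no other verification step in the Protocol, the natural reading is that a patient with a negative week-8 biopsy goes into the no-residual-disease column. A biopsy samples tissue and can miss tumour. Where that happens, the patient is filed wrongly, and the direction of the error depends on the NBI result:

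- In an NBI non-suspicious patient, a false negative for NBI becomes a true negative, so NPV is too high.
- In an NBI-suspicious patient, a true positive becomes a false positive, so PPV and specificity are too low.

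NPV is the figure that would be used to reassure a patient whose NBI is clean, so an error in the favourable direction matters most there. A single table cannot show either effect.

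Sensitivity is a separate matter, because it depends on how the misses divide between the two NBI groups. If the operator samples what NBI shows, a suspicious area offers a target that a non-suspicious nasopharynx does not, and misses could cluster in the non-suspicious group. Recording what prompted each sample would show whether this happens. The plan does not ask for it.

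**Working it through.** **The plan's own figures.** There is nothing to reproduce. The target of 50-70 patients has no derivation, and no residual rate, NBI accuracy or biopsy miss rate is given. The values below are assumptions chosen to show direction and rough size.

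**Assumed inputs.** N = 60 (within 50-70), residual rate 10%, true NBI sensitivity 0.70, true specificity 0.85, no false-positive biopsies. Let m+ and m- be the shares of true residual tumours that biopsy misses in NBI-suspicious and NBI non-suspicious patients.

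**True table.** Residual cases are 60 x 0.10 = 6, and non-residual 54. TP = 6 x 0.70 = 4.2; FN = 1.8; TN = 54 x 0.85 = 45.9; FP = 8.1. NBI-suspicious total 12.3; non-suspicious total 47.7. True PPV = 4.2/12.3 = 0.341; true NPV = 45.9/47.7 = 0.962.

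**Observed values with biopsy as the only reference.**

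- Sensitivity = TP(1 - m+) / [TP(1 - m+) + FN(1 - m-)]
- NPV = 1 - FN(1 - m-)/47.7
- PPV = TP(1 - m+)/12.3
- Specificity = [TN + FN x m-] / [54 + TP x m+ + FN x m-]

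| m+ | m- | Sensitivity | Specificity | PPV | NPV |
|---|---|---|---|---|---|
| 0 | 0 (true) | 0.700 | 0.850 | 0.341 | 0.962 |
| 0.1 | 0.1 | 0.700 | 0.844 | 0.307 | 0.966 |
| 0.3 | 0.3 | 0.700 | 0.832 | 0.239 | 0.974 |
| 0.1 | 0.3 | 0.750 | 0.845 | 0.307 | 0.974 |
| 0.1 | 0.5 | 0.808 | 0.846 | 0.307 | 0.981 |
| 0.3 | 0.1 | 0.645 | 0.831 | 0.239 | 0.966 |

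Example, fifth row: sensitivity = 4.2 x 0.9 / (4.2 x 0.9 + 1.8 x 0.5) = 3.78/4.68 = 0.808; NPV = 1 - 0.9/47.7 = 0.981.

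**Reading the table.**

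1. NPV rises whenever m- > 0, whatever m+ is. The residual rate among NBI non-suspicious patients is understated by exactly the fraction m-: from 1.8/47.7 = 3.8% to 1.9% when m- = 0.5.
2. PPV falls by exactly the fraction m+. Misses in suspicious patients also lower specificity; misses in non-suspicious patients raise it slightly. With m+ = 0 and m- = 0.5 it is 46.8/54.9 = 0.852.
3. Sensitivity is unchanged when m+ = m-, rises when m- > m+, and falls when m- < m+.

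**Other residual rates** (sensitivity 0.70, specificity 0.85, m- 0.1 to 0.5, m+ 0.1 or 0.3). At 5%, NPV reads 0.984 to 0.991 against 0.982, and PPV 0.177 or 0.138 against 0.197. At 20%, NPV reads 0.927 to 0.959 against 0.919, and PPV 0.485 or 0.377 against 0.538.

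**How later histology would move the figures.** Take 6 NBI-suspicious patients among 7 biopsy-positive. If follow-up finds tumour in one biopsy-negative patient who was NBI-suspicious, sensitivity goes from 6/7 (86%) to 7/8 (88%). If that patient was NBI non-suspicious, it goes to 6/8 (75%). NPV can only stay or fall, and PPV can only stay or rise.

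**Timing.** If the last week-8 biopsy falls no later than the planned end of follow-up (4/2017), a 6-month window closes by 10/2017, one month before the 11/2017 presentation.

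**The case against.** A reader might infer that NBI sensitivity is inflated. The documents do not support that as a fact. Method item 5 places endoscopy and biopsy at the same visit but never says that NBI directs the site. White light is used at the same visit and baseline images are stored, so either could guide sampling too. Equal misses leave sensitivity at 0.700, and the opposite pattern lowers it to 0.645. This objection stands, and the sensitivity claim is conditional.

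A reader might also infer that the SAP defines residual disease by biopsy alone. It gives no definition. That biopsy fills the disease column is an inference from the absence of any other verification step. The documentable gap is the missing definition.

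Nor is the same-session biopsy a fault. The biopsy appointment is arranged at week 2, before the week-8 NBI, and is planned for every patient. That avoids partial verification, and the shared visit avoids change in disease between the two tests. Both are strengths.

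The remaining objections concern follow-up and precision. The stated purpose of joint follow-up is not disease surveillance, and planned follow-up ends 4/2017, so later histology may be incomplete. This limits how the secondary table can be read but does not remove its use. Sampling error is also larger than the bias in most scenarios: with 6 residual cases, a rough 95% half-width for a sensitivity of 0.70 is 1.96 x sqrt(0.70 x 0.30/6) = 0.37. That is true, but a confidence interval would not reveal a misclassified reference, and the direction of the NPV error is known in advance.

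**Conclusion.** The concern holds for NPV, PPV and specificity, and only conditionally for sensitivity. The week-8 biopsy is the only reference the plan describes, the SAP leaves residual disease undefined, and nothing checks a negative result.

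On the assumed inputs at 10% residual disease, NPV is overstated by 0.4 to 1.9 percentage points and PPV understated by 3.4 or 10.2 points. At 20%, NPV is overstated by 0.8 to 4.0 points. Sensitivity could read anywhere from 0.645 to 0.808 against a true 0.70, depending on a sampling pattern that the plan neither states nor records. With 50-70 patients and an assumed residual rate of 5% to 20%, between 50 x 0.05 = 2.5 and 70 x 0.20 = 14 residual cases are expected, so one or two misfiled tumours would visibly move the sensitivity estimate.

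The directions for NPV and PPV follow from the structure of the table, provided there are no false-positive biopsies. The sizes rest wholly on the assumed rates. This should be fixed because the remedy is cheap. It does not invalidate the design.

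**What to change.** Leave the biopsy practice as it is.

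1. In SAP item 3, define residual disease in the main table as a positive week-8 biopsy. Add a pre-specified secondary 2x2 table in which a biopsy-negative patient also counts as residual if routine ENT or oncology records show histologically confirmed mucosal nasopharyngeal tumour within 6 months of that biopsy. Report sensitivity, specificity, PPV and NPV from both tables, and the number of patients with less than 6 months of records. State that absence of later histology is not proof of no disease.
2. On the week-8 template, record each sample's site and whether white light, NBI or neither prompted it. Tabulate biopsy results by prompt.
3. Describe the biopsy-only NPV as a likely upper limit. For sensitivity, report the direction of change between the two tables and do not call it an upper limit.

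The cost is one SAP paragraph, one template addition and a records review, with no extra biopsy or visit. There are three downsides. The window runs past the planned end of follow-up, so records may be incomplete and time before the presentation is short. A later tumour may be early recurrence, not residual disease. A later biopsy may itself have been prompted by the earlier NBI result. For these reasons the biopsy-only table remains the main one.
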